8.0 ADVERSE EVENTS AND POTENTIAL RISKS

8.1 Radiation Therapy

All patients will be seen weekly by their treating radiation oncologist while undergoing EBRT. Any observations with respect to the following symptoms/side effects will be recorded:

- Bowel/rectal irritation manifesting as cramping, diarrhea, urgency, proctitis, or hematochezia
- Urinary frequency, urgency, dysuria, hematuria, urinary tract infection, or incontinence
- Radiation dermatitis

Clinical discretion may be used in managing radiotherapy-related side effects. Diarrhea/rectal frequency/urgency may be managed with diphenoxylate or loperamide. Bladder irritation may be mitigated with phenazopyridine. Urinary frequency/urgency can be managed with anticholinergic agents or alpha-blockers such as tamsulosin. Erectile dysfunction can be managed with phosphodiesterase (PDE) inhibitors such as sildenafil.

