Sample Size	Number expected to accrue: 5 Age: ≥ 18 Gender: Male and Female
Disease sites/Conditions	Esophagus / Esophageal Cancer
Interventions	Agent/Route: Endoesophageal Brachytherapy Cycle Length: Weekly Number of cycles: Between 3 and 6 cycles

ABBREVIATIONS

CCCC	Case Comprehensive Cancer Center
CRF	Case Report Form
DCRU	Dahm's Clinical Research Unit
DSTC	Data Safety and Toxicity Committee
FDA	Food and Drug Administration
ICF	Informed Consent Form
IRB	Institutional Review Board
PRMC	Protocol Review and Monitoring Committee
SOC	Standard of Care
CCF	Cleveland Clinic Foundation
UH	University Hospitals
IPC	Innovative Practice Committee

TABLE OF CONTENTS

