1.4 Rationale

Although patient access to endoscopy centers has expanded and the incidence of esophageal cancer continues to increase, one of the key limiting factors in the more widespread use of esophageal brachytherapy is the limitations of the current single catheter approach. Therefore, in an effort to improve on this technique, patients in our department have been treated using a novel 3-tube technique. This 3-tube technique makes the dose more conformal and reduces the "hot spots" of radiation (doses above the prescription dose) in the esophageal wall. We evaluated the clinical outcomes of the initial thirteen patients treated for medically unresectable, stage 0-IVA, esophageal cancer with our 3-tube design: Five patients were treated with HDR brachytherapy alone and eight were treated with a combination of HDR brachytherapy and external beam radiation therapy. Across all patients, the 18-month local control, disease-free-survival, and overall survival rates were 81%, 74%, and 92%, respectively. Moreover, no patients have suffered a fistula as a result of treatment and only two patients have required dilation for esophageal strictures. A majority of the patients (11 of 13) continue to be free of dysphagia at a median of 17 months of follow-up. These promising initial results have fueled our interest in further innovation of our delivery technique in an effort to broaden the utility of esophageal brachytherapy as well as provide more effect cancer-directed therapy while maintaining a patient's quality of life.

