2.2 Secondary Objective(s)

- a.** To collect data in order to show how the 6-tube endoesophageal brachytherapy technique will be an improvement (more conformed dose distribution) over our previously designed 3-tube endoesophageal brachytherapy technique in patients who are candidates for esophageal brachytherapy
- b.** To evaluate acute toxicity of novel endoesophageal brachytherapy applicator.

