3.4 Expected Duration of Treatment and Subject Participation

The initial treatment session will occur after the patient has been found to be eligible, the consent form has been completed, and the treatment plan has been created. The patient will undergo subsequent weekly treatments for 3 to 6 weeks after the initial treatment.

The subject will be expected to participate in the trial throughout its entirety. The participation period is 6 months of which the patient will be evaluated and seen at months 3 and 6.

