6.0 TREATMENT PLAN

6.1 Radiation Therapy

6.1.1 General Guidelines and Timing

Radiation therapy treatment planning

Patients will be planned using our standard 3D, CT-based, Oncentra treatment planning system. The target volume will be identified during endoscopy and an approximately 2 cm proximal and distal margin will be added to account for microscopic tumor extension (beyond the gross macroscopic disease) and to account for any spatial inaccuracy of the applicator device positioning. The dose will be prescribed to treat the target volume with modification if necessary to decrease doses to the normal surrounding tissues.

Intraoperative procedure

In the operating room, the patient's pulse, pulse oximetry, and blood pressure are obtained prior to the procedure and during the procedure. The patient is typically medicated with Demerol (100 mg IV) and Versed (4 mg IV) throughout the procedure and Benzocaine topically prior to the procedure as per standard anesthesia practices for esophageal brachytherapy patients. The endoscope is passed through the mouth under direct visualization and advanced distally, typically to the stomach or 2nd portion of the duodenum. The scope is then gradually withdrawn and the mucosa is examined. Of note, if a significant area of stenosis is identified, this is dilated to allow for a sufficient diameter for insertion of the brachytherapy applicator. Once the cancerous mucosa is visualized, radio-opaque markers (endoclips or metallic seeds) are placed with ~2 cm margins on the proximal and distal ends of the tumor. A guidewire is then passed to the stomach and the endoscope is removed. Over the guidewire, the brachytherapy applicator device is then placed under fluoroscopic guidance ensuring that the distal end travels past the most distal radio-opaque endoclip and typically into the stomach. The brachytherapy applicator is then stabilized and secured by inflating the anchor balloon and/or fixing to the mouth guard after removal of the guidewire.

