6.1.2 Equipment and Techniques to be used

After applicator placement, the patient is transported to the Department of Radiation Oncology for a CT simulation. Metal dummy seeds are placed into the channels. The treatment balloon is inflated to move the channels in close proximity to the esophageal tumor. The patient is placed in the supine position and undergoes a planning CT scan of the neck and thorax. The CT images are downloaded into the Oncentra treatment planning system and then tumor volume as well as normal critical structures are outlined by the treating radiation oncologist. During the treatment planning phase, the patient is transported to the nursing unit for observation. Following completion of treatment planning, the patient is transported to the HDR brachytherapy treatment room and maintained on the transport cart in the supine position. The exterior portions of the brachytherapy channels are connected to the remote afterloader HDR device. AnIridium-192 seed will enter the channels to deliver the planned course of brachytherapy. After treatment delivery, the brachytherapy channels are disconnected from the HDR afterloader device. After deflation of the anchor and treatment balloons and disconnection from the mouthpiece the multichannel applicator is removed gently from the patient. No devices will remain in the patient. The patient is subsequently transported to the nursing unit for vital sign monitoring for approximately one-half hour prior to discharge to home.

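### Section 8.1 lists side effects of another body site, so graded, non-serious acute esophageal and insertion-related events are not specifically prompted in the protocol text

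*Combined protocol and SAP*

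**What the plan says.** The Protocol Summary gives the intervention as "Agent/Route: Endoesophageal Brachytherapy". Section 2.2 makes toxicity a secondary objective: "To evaluate acute toxicity of novel endoesophageal brachytherapy applicator". Section 3.0 lists acute toxicity as data item H, without detail.

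Section 8.1 sets the observation schedule: "All patients will be seen weekly by their treating radiation oncologist while undergoing EBRT". The effects to be recorded there fall into three groups. The first is "Bowel/rectal irritation manifesting as cramping, diarrhea, urgency, proctitis, or hematochezia"; the others are urinary symptoms and radiation dermatitis. The management text that follows deals with diarrhea, bladder irritation, urinary frequency and erectile dysfunction. Sections 9.0 and 13.0 both send the reader to Section 8 for adverse event lists.

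Other parts of the plan also collect toxicity:
- Section 3.0 and Appendix II record esophageal ulceration, fistula, stricture and need for dilation as Yes/No. Section 12.0 repeats the four items.
- Section 8.3.3 requires all adverse events seen by the team or reported by the subject after consent to be recorded with CTCAE term, grade, dates and attribution.
- Section 13.1 says that the calendar and required forms are in OnCore. They are not part of the documents.

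**The concern.** A secondary objective depends on acute toxicity data, and the one section that names symptoms to look for names those of a pelvic field. An investigator who follows Section 8.1 literally would record bowel and bladder effects and would not be reminded of pain, esophagitis, worsening dysphagia or effects of inserting the applicator. Non-serious events of that kind would then enter the data when someone notices or volunteers them, rather than because they are asked about at set times and graded. With about 5 patients, a descriptive toxicity table built that way could look cleaner than the patients' experience.

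Three leftovers of template text in the same part of the protocol add ambiguity:
- All five attribution categories in 8.3.3 refer to a study drug, although the title page lists agents and IND as not applicable.
- An instruction at the end of 8.3.3, to state whether attribution is to components or to the whole regimen, is unanswered.
- The start of the reporting period in 8.5 is an unfilled placeholder.

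**Working it through.** The plan states no toxicity figure to reproduce. The check is a comparison of sections and one timing calculation.

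**1. What is prompted, and where**

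| Place | What it covers | Esophageal or insertion events named | Grade |
|---|---|---|---|
| 8.1 | Bowel/rectal, urinary, skin | 0 of 3 groups | Not stated |
| 3.0, item H | Acute toxicity, no detail | None | Not stated |
| 3.0 items J–M, 12.0, Appendix II | Ulceration, fistula, stricture, dilation | 4 items | Yes/No (3.0, Appendix II) |
| 8.3.3 | Every event observed or reported after consent | None named | CTCAE 4.0 |

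Appendix II has columns for record number, date, tumor response and the four Yes/No items. It has none for acute toxicity, grade, onset or attribution. Taken together, the rows show that a graded, non-serious event other than the four Yes/No items has a place to be recorded (8.3.3, item H). Nothing in the protocol text names it or fixes when it is asked about.

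**2. Treatment named in 8.1 against treatment planned**

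Section 6.1 covers endoscopy, applicator placement, CT planning and HDR delivery, with no EBRT. Section 4.2 does not exclude EBRT, so some patients may receive it. Even for them, the 8.1 list does not name the esophagus, and the visit sentence is not tied to the brachytherapy sessions.

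**3. Is there a scheduled visit in the 30 days after the last fraction?**

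Section 8.5 ends the reporting period 30 days after the final dose. Section 3.4 fixes follow-up: "The participation period is 6 months of which the patient will be evaluated and seen at months 3 and 6".

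Inputs: weekly sessions (3.4, 6.1.3, 11.2); follow-up counted from the initial procedure (6.8); a window of 7 days either side of the month 3 visit and 1 day for treatment visits (11.2). Assumption: month 3 is 91 days after day 1, the first session.

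- Earliest month 3 visit: day 1 + 91 − 7 = day 85.
- Last session, for s sessions: day 1 + 7(s − 1).
- Gap: 85 − [1 + 7(s − 1)].

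The session count is stated differently in different places (3 to 6 in the Protocol Summary, 2 to 6 in 6.1.3), so a range is shown:

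| Sessions s | Last session | Gap to earliest visit |
|---|---|---|
| 2 | Day 8 | 77 days |
| 3 | Day 15 | 70 days |
| 6 | Day 36 | 49 days |
| 7 (one reading of 3.4, in conflict with 6.7) | Day 43 | 42 days |

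Taking month 3 as 89 to 92 days shifts each gap by −2 to +1 days, and the treatment window shifts it by 1 day. The smallest gap is then 42 − 2 − 1 = 39 days. If month 3 is counted from the last fraction, the gap is 91 − 7 = 84 days. Every case exceeds 30 days, so the protocol text schedules no visit in that period.

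**The case against.** The strongest reply is that collection is broader than 8.1, and much of this reply stands. Acute toxicity is a data item in its own right. Section 3.0 also collects the endoscopy video and comments from the treatment team, and Sections 3.0 and 14.0 plan to relate endoscopic follow-up images to dose. At each procedure "The scope is then gradually withdrawn and the mucosa is examined", and after treatment there is "vital sign monitoring for approximately one-half hour prior to discharge to home". Sections 6.8 and 8.5 require recognised events to be followed, and serious events have their own reporting route. A reader might infer from 8.1 that esophageal toxicity goes uncollected; these provisions rule that out. They do not make the text name other acute symptoms or say when they are graded.

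A reader might also infer that patients given brachytherapy alone lose data because the visit sentence mentions only EBRT. The earlier 3-tube series had both kinds of patient: "Five patients were treated with HDR brachytherapy alone and eight were treated with a combination of HDR brachytherapy and external beam radiation therapy". But being outside a sentence that prompts mostly the wrong organs loses little esophageal information, and those patients still attend the brachytherapy sessions. The share treated with brachytherapy alone therefore does not measure lost data.

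Nor does the study-drug wording cause events to be missed. The item list in 8.3.3 refers to the therapy or agent, so the intended meaning can be inferred. The wording leaves attribution ambiguous, as the blank in 8.5 does for the reporting start.

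Finally, radiation dermatitis is not confined to pelvic treatment, and the OnCore forms may hold a suitable list. Both points are fair. The second means that the mismatch in the protocol text is certain, while under-ascertainment is only possible.

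**Conclusion.** The point holds in limited form. Section 8.1 is unadapted text for another body site, and it sits where the protocol sends readers for adverse event lists. Graded, non-serious acute esophageal and insertion-related events are not specifically prompted in the protocol text and may be under-ascertained, which bears on the secondary toxicity objective. After the last fraction, the first scheduled visit comes at the earliest 49 to 70 days later for 3 to 6 sessions, given exact weekly spacing and month 3 counted from the first session.

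How many events would be missed cannot be derived from the documents. The dosimetric primary objective is unaffected, and a descriptive toxicity summary remains possible. Severity is minor to moderate.

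**What to change.** 1. Replace the 8.1 list with esophageal, thoracic and applicator or insertion terms from CTCAE v4.0. Have them graded at baseline, at each brachytherapy session and at the existing month 3 and 6 visits. Add acute toxicity grade, onset and attribution to Appendix II, or confirm that the OnCore forms hold them.
2. As clean-up, change study drug to study treatment in 8.3.3 and answer the open instruction on component or whole-regimen attribution. Fill in the 8.5 start so that it agrees with 8.3.3 and includes insertion-related events. State how events in the 30 days after the last fraction are ascertained. A telephone contact, or recall and records at month 3, would each serve; the choice is the sponsor's.
3. Reconcile the pelvic management text in 8.1 with the treated site. No clinical rule is proposed here.

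The cost is protocol wording and a check of the forms. The graded assessments use sessions and visits already planned. The downside is a few more adverse event entries per patient. Precision with about 5 patients does not change.

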8.3 Definitions

8.3.1 Adverse Event

An **adverse event** (AE) is any unfavorable or unintended event, physical or psychological, associated with a research study, which causes harm or injury to a research participant as a result of the participant's involvement in a research study. The event can include abnormal laboratory findings, symptoms, or disease associated with the research study. The event does not necessarily have to have a causal relationship with the research, any risk associated with the research, the research intervention, or the research assessments.

Adverse events may be the result of the interventions and interactions used in the research; the collection of identifiable private information in the research; an underlying disease, disorder, or condition of the subject; and/or other circumstances unrelated to the research or any underlying disease, disorder, or condition of the subject.

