8.3.2 Serious Adverse Events

A **serious adverse event** (SAE) is any adverse experience occurring at any dose that results in any of the following outcomes:

- Results in **death**.
- Is a **life-threatening** adverse experience. The term life-threatening in the definition of serious refers to an adverse event in which the subject was at risk of death at the time of the event. It does not refer to an adverse event which hypothetically might have caused death if it were more severe.
- Requires **inpatient hospitalization or prolongation of existing hospitalization**. Any adverse event leading to hospitalization or prolongation of hospitalization will be considered as Serious, UNLESS at least one of the following expectations is met:
 - The admission results in a hospital stay of less than 24 hours OR
 - The admission is pre-planned (e.g., elective or scheduled surgery arranged prior to the start of the study) OR

- The admission is not associated with an adverse event (e.g., social hospitalization for purposes of respite care).

However it should be noted that invasive treatment during any hospitalization may fulfill the criteria of “medically important” and as such may be reportable as a serious adverse event dependant on clinical judgment. In addition where local regulatory authorities specifically require a more stringent definition, the local regulation takes precedent.

- Results in **persistent or significant disability/incapacity**. The definition of disability is a substantial disruption of a person’s ability to conduct normal life’s functions.
- Is a **congenital anomaly/birth defect**.
- Is an **important medical event**. Important medical events that may not result death, be life-threatening, or require hospitalization may be considered a serious adverse experience when, based upon appropriate medical judgment, they may jeopardize the subject and may require medical or surgical intervention to prevent one of the outcomes listed in this definition. Examples of such medical events include allergic bronchospasm requiring intensive treatment in an emergency room or at home, blood disease or disorders, or convulsions that do not result in inpatient hospitalization, or the development of drug dependency or drug abuse. The development of a new cancer is always considered an important medical event.

For the purpose of this study the following events would not be considered adverse events and would not be recorded in the database:

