- Abnormal laboratory findings considered associated to the original disease

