8.3.3 Adverse Event Evaluation

The investigator or designee is responsible for ensuring that all adverse events (both serious and non-serious) observed by the clinical team or reported by the subject which occur after the subject has signed the informed consent are fully recorded in the subject’s medical records. Source documentation must be available to support all adverse events.

A laboratory test abnormality considered clinically relevant (e.g., causing the subject to withdraw from the study, requiring treatment or causing apparent clinical manifestations, result in a delay or dose modification of study treatment, or judged relevant by the investigator), should be reported as an adverse event.

The investigator or sub-investigator (treating physician if applicable) will provide the following for all adverse events (both serious and non-serious):

- Event term (as per CTCAE)
- Description of the event
- Date of onset and resolution
- **Expectedness of the toxicity**
- **Grade of toxicity**
- **Attribution of relatedness to the investigational therapy/agent- (this must be assigned by an investigator, sub-investigator, or treating physician)**
- Action taken as a result of the event, including but not limited to; no changes, dose interrupted, reduced, discontinued, etc. or action taken with regard to the event, i.e. no action, received conmed or other intervention, etc.
- Outcome of event

Descriptions and **grading scales** found in the NCI Common Terminology Criteria for Adverse Events (CTCAE) version **4.0** will be utilized for agent AE reporting.

An expected adverse event is an event previously known or anticipated to result from participation in the research study or any underlying disease, disorder, or condition of the subject. The event is usually listed in the Investigator Brochure, consent form or research protocol.

An unexpected adverse event is an adverse event not previously known or anticipated to result from the research study or any underlying disease, disorder, or condition of the subject.

Attribution is the relationship between an adverse event or serious adverse event and the study drug. Attribution will be assigned as follows:

- Definite – The AE is clearly related to the study drug.
- Probable – The AE is likely related to the study drug.
- Possible – The AE may be related to the study drug.
- Unlikely – The AE is doubtfully related to the study drug.
- Unrelated – The AE is clearly NOT related to the study drug.

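### Sections 8.3.2 and 8.3.3 give opposite instructions for a clinically relevant laboratory abnormality attributed to the tumor, and the first sentence of 8.3.1 does not match the rest of the adverse-event rules

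*Combined protocol and SAP*

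**What the plan says.** Four pieces of text in section 8.3 of the combined protocol and SAP bear on what is recorded.

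- **8.3.1, first sentence.** An AE is an event "which causes harm or injury to a research participant as a result of the participant's involvement in a research study".
- **8.3.1, remainder.** "The event can include abnormal laboratory findings, symptoms, or disease associated with the research study". Then: "The event does not necessarily have to have a causal relationship with the research". The next paragraph accepts as possible sources "an underlying disease, disorder, or condition of the subject; and/or other circumstances unrelated to the research".
- **8.3.2, closing lines.** "For the purpose of this study the following events would not be considered adverse events and would not be recorded in the database". One item follows: "Abnormal laboratory findings considered associated to the original disease". It carries no limit on grade, change from baseline or clinical consequence.
- **8.3.3.** "A laboratory test abnormality considered clinically relevant (e.g., causing the subject to withdraw from the study, requiring treatment or causing apparent clinical manifestations", and also one that delays or modifies study treatment or that the investigator judges relevant, should be reported as an AE. Nothing is said about presumed cause.

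Section 8.3.3 also requires all AEs after consent to be in the medical records, and gives an attribution scale that runs from definite to unrelated. Section 2.2 makes acute toxicity secondary objective b, and section 3.2 plans about 5 subjects.

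**The concern.** The 8.3.2 exclusion turns on a judgment of cause, and the 8.3.3 rule turns on clinical consequence. Where a finding meets both, staff have two opposite instructions. If they follow 8.3.2, the finding is not an AE and has no database entry, so it never reaches the attribution scale and cannot be re-attributed later.

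The overlap is plausible in this disease. Section 1.1 mentions tumor hemorrhage, from institutional series, as a reason to use brachytherapy, and ulceration is an outcome collected in this study. Either could lower hemoglobin. What is at stake is the completeness of the acute-toxicity result for a new applicator. An omission can only move that result toward fewer events.

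**Working it through.** The documents state no toxicity rate, so there is no figure to reproduce. The check is a comparison of rules, followed by a note on scale.

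**Step 1: 8.3.2 against 8.3.3 for a laboratory abnormality.**

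| Clinically relevant? | Attributed to tumor? | 8.3.2 | 8.3.3 | Outcome |
|---|---|---|---|---|
| Yes | Yes | Not an AE, not recorded | Report as AE | Conflict |
| Yes | No | Silent | Report as AE | Reported |
| No | Yes | Not an AE, not recorded | Silent | Not recorded |
| No | No | Silent | Silent | General definition in 8.3.1 |

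Only the first row conflicts. Reading the specific rule as overriding the general one does not settle it. One rule is defined by cause and the other by consequence, so neither is a special case of the other. The text states no precedence.

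The duty in 8.3.3 to document AEs in the medical records does not settle it either, because under 8.3.2 the finding is not an AE.

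**Step 2: 8.3.1 against itself and against 8.3.3.** The opening sentence requires that the harm result from participation. Two sentences later no causal relationship is needed, and underlying disease is then named as a source. The attribution scale in 8.3.3 includes unlikely and unrelated, and its definition of an expected event covers events from the subject's underlying disease. Those categories would have no use if only harm caused by participation counted. The section as a whole therefore points to recording regardless of cause, and the opening sentence is the odd one out.

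**Step 3: other places where an omitted finding might still appear.** Section 3.0 (items J to M), section 12.0 and Appendix II collect ulceration, fistula, stricture and need for dilation as separate items, with no test of cause. Appendix II has no column for bleeding, hemoglobin or general toxicity. The side-effect list in 8.1 covers bowel, urinary and skin effects, with no hematologic item. Laboratory consequences are therefore not picked up elsewhere.

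**Step 4: scale.** Input: n = 5 (section 3.2). A patient whose only event is omitted changes the observed rate by 1/5 = 20 percentage points. Exact (Clopper-Pearson) 95% intervals:

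- 1 of 5: 20%, interval 0.5% to 71.6%.
- 0 of 5: 0%, upper limit 1 − 0.025^(1/5) = 52.2%.

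This is arithmetic that holds for any omitted event in five patients. It is not an estimate of how many would be omitted.

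**The case against.** The strongest reply is that the plan, read whole, already records events whatever their cause. Most of 8.3.1 says so, 8.3.3 provides for unrelated events, and 8.5 covers all AEs through 30 days after the last dose. This answers most of the worry about 8.3.1. It does not answer 8.3.2, which removes a class of findings before those provisions apply.

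A reader might infer that bleeding drops out of the toxicity result. The documents do not support that. The exclusion covers laboratory findings only, and bleeding is a clinical event. It would be lost only if the first sentence of 8.3.1 were used in isolation, against the text that follows it. Nor would a fistula or ulcer be lost, since each has its own yes/no item.

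A reader might also infer that sites will record differently. Section 5.0 registers all subjects through one center, and the multi-site wording in 8.5.1 names no second enrolling site. Different recording by different staff remains possible.

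Three further limits stand. The verb in 8.3.3 is should, not must, and it applies only to clinically relevant abnormalities. The readable text, including section 11.2, schedules no laboratory tests, so findings would come from tests done for other reasons. Section 14.0 sets no toxicity threshold or formal toxicity test, so no stated decision turns on a single event.

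**Conclusion.** The point holds in a limited form. There is one real conflict: a laboratory abnormality that is both clinically relevant and attributed to the tumor is excluded by 8.3.2 and reportable under 8.3.3. Treated anemia is the natural example. There is also one inconsistency of wording, in the first sentence of 8.3.1, which the rest of the section largely corrects.

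The possible error in secondary objective b runs toward too few events. Its size is unknown, because the documents give no basis for counting such findings; 20 percentage points per patient affected is the scale only. The conclusion assumes that acute toxicity will be summarized from the AE records, since no separate source is defined for it. It also assumes that laboratory tests are done in routine care. The documents do not show that bias will occur, only that the rules permit it.

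**What to change.** **Section 8.3.2.** State that the exclusion does not apply to any laboratory abnormality that meets the clinical-relevance test in 8.3.3 or has worsened in CTCAE grade from baseline. State that these are recorded whatever the presumed cause, with causality handled by the attribution scale in 8.3.3.

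**Section 8.3.1.** Reword the first sentence so that an AE is any unfavorable or unintended event after consent, whether or not it is related to the research. Both restrictions must go: the clause quoted above and the earlier words that tie the event to a research study. Removing the quoted clause up to its end but keeping the earlier tie would still limit AEs to study-associated events.

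**Cost.** Two changes of wording and a few more disease-related entries in the AE listing. No change to sample size, visits or treatment is needed.
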